## Statistical Analysis Plan

**Sponsor:** Island Pharmaceuticals Ltd  
**Protocol Number:** ISLA101-P01-CT001

The plasma concentrations of fenretinide and its metabolites N-(4-methoxyphenyl) retinamide (MPR) and 4-oxo-N-(4-hydroxyphenyl) retinamide (oxo-HPR) will be determined using a validated analytical procedure. Specifics about the analytical method will be provided in the bioanalysis report. Concentrations data will be provided electronically by the analyzing laboratory.

Concentrations that are below limit of quantification (BLQ) prior to the first measurable concentration will be set to zero for all calculation and analyses. BLQ concentrations observed after the first measurable concentration will be treated as missing. In addition to statistical descriptors, number of BLQ concentrations will be presented in the summary for each treatment and time point.

### 4.3 Pharmacokinetic Parameters

The PK parameters described in this section will be derived based on the plasma concentration-time profiles of fenretinide, MPR and oxo-HPR as observed after the study drug administrations on Day 1 for Cohort 1-3 and Day 10 for Cohort 4 if the data permits using actual timepoints for PK samples. The parameters will be calculated separately for each cohort based on concentrations collected during the specific period.

The PK concentrations will be processed using standard noncompartmental analytical procedures to derive the required parameters. The software used for the analysis will be Phoenix™ WinNonlin® v8.4.0 or greater (Certara, Princeton NJ, USA). Extravascular plasma model with linear up log down trapezoidal rule will be utilized.

The PK parameters described in Table 4 will be derived for the analytes (fenretinide, MPR and oxo-HPR) provided that the required concentration data are available. Supporting PK parameters (used to derive or assess the validity of  $\lambda_z$  and associated parameters) which include Adjusted R^2, number of points for estimation of  $\lambda_z$  or Kel, %AUCextrap and span (ratio of time interval to estimate  $\lambda_z$  to t1/2) will only be listed and not included in the summary tables. %AUCextrap < 20% will be used to validate AUCinf and parameters derived from AUCinf.

**Table 4 Plasma PK Parameters**

Parameter	Definition
C max	Maximum concentration which is directly determined from the plasma concentration-time profiles.
T max	Time to maximum observed plasma concentration. If the same C max concentration occurs at different time points, T max is assigned to the first occurrence of C max .
AUC inf	The area under the plasma concentration-time curve from time 0 (time of dosing) extrapolated to infinity. AUC inf is calculated as the sum of AUC last plus the ratio of the last measurable plasma concentration (C last ) to the elimination rate constant ( $\lambda_z$ ), calculated by 'the linear up and log down' method.
AUC last	Area under the drug concentration-time curve, from time 0 (time of dosing) to the last measurable concentration.
AUC 0-24	The area under the plasma concentration-time curve, from time 0 (time of dosing) to 24 hours, calculated by 'the linear up and log down' method.
$\lambda_z$ or kel	Apparent terminal elimination rate constant calculated by linear regression of the terminal linear portion of the log concentration vs. time curve.
T 1/2	Apparent plasma terminal half-life calculated as ln (2)/ $\lambda_z$ .
C L/F	Apparent total plasma clearance, using the following formula: Dose/AUC inf (Parent compound only).

**Statistical Analysis Plan**

**Sponsor:** Island Pharmaceuticals Ltd  
**Protocol Number:** ISLA101-P01-CT001

Parameter	Definition
Vz/F	Apparent volume of distribution, using the formula: C L /F/λ z (Parent compound only).
DN_C max	Dose-normalised C max will be calculated by dividing C max by the total administered dose in mg (C max /Dose).
DN_AUC inf	Dose-normalised AUC 0-inf will be calculated by dividing AUC inf by the total administered dose in mg (AUC inf /Dose).
DN_AUC last	Dose-normalised AUC 0-last will be calculated by dividing AUC last by the total administered dose in mg (AUC last /Dose).
Adjusted R  (*)	R-squared adjusted.
No. of Points (*)	Number of points for determination of λ z .
Span(*)	Span = (λ z upper - λ z lower )/ t 1/2 (h).
AUC%extrap(*)	The percentage of the AUC that has been extrapolated beyond the last observed data point, using the following formula, calculated by 'the linear up and log down' method

Values for λz, t1/2, AUCinf, CL/F and Vz/F will not be reported for cases that do not exhibit an acceptable terminal log-linear phase in the concentration versus time profile. Additional pharmacokinetic parameters may be determined where appropriate.  
 (\*) Derived to determine t1/2, results will only be listed.

λz and T1/2, will only be included in the summary statistics if the following criteria are met:

- A minimum of 3 measurable concentration-time points is available during log-linear portion of the terminal elimination phase (excluding Cmax), i.e., No. of Points is ≥ 3.
- Adjusted R^2 > 0.80.

AUCinf, CL/F and Vz/F will only be included in the summary statistics if the following criterion is met:

- %AUCextrap < 20%.
- Span ≥ 2

## 4.4 Baseline Characteristics and Other Measures

### 4.4.1 Subject Disposition

Subject disposition data will be collected on the 'End of Study Participation' eCRF when a subject completed or early terminated the study.

The following data will also be presented in the disposition listing:

- Date of informed consent ('Informed Consent' eCRF),
- Date/time of the first study drug administrations ('Study Drug Administration' eCRF.)

The number of subjects included in the analysis sets defined in Section 3 will be summarized and presented as part of the subject disposition data.

### 4.4.2 Protocol Deviations and Eligibility

Protocol deviations will be reported on the 'Protocol Deviation' eCRF.

Protocol deviations will be grouped by deviation grade (minor/major), deviation term, assessment type, and a description of the deviation will also be noted.

Eligibility will be reported on the 'Eligibility Confirmation' eCRF.

**Statistical Analysis Plan**

**Sponsor:** Island Pharmaceuticals Ltd  
**Protocol Number:** ISLA101-P01-CT001

The eligibility of all subjects for entry into the study will be assessed at Screening and Day -1 (For Cohort 1-3)/Day 9 (for Cohort 4). A subject should have met all the inclusion, and none of the exclusion criteria before entry into the study.

**4.4.3 Demographics**

Demographic information provides data about the subjects and is necessary to determine whether the individuals in the study are a representative sample of the target population.

The following demographic data will be collected on the 'Demography' eCRF at Screening.

- Year of birth
- Age (Years)
- Sex ('Male', 'Female')
- Childbearing Potential (Yes/No) -If yes, the menopausal status
- Ethnicity ('Hispanic or Latino', 'Not Hispanic or Latino', 'Not Reported', 'Unknown')
- Race:
  - 'White'
  - 'Black or African American'
  - 'Asian'
  - 'American Indian or Alaska Native'
  - 'Native Hawaiian or Other Pacific Islander'
  - 'Other'
  - 'Not Reported'
  - 'Unknown'

**4.4.4 Baseline Subject Characteristics**

Baseline subject characteristics include characteristics that subjects presented with prior to the administration of study drug.

The following subject characteristics will be collected on the 'Vital Signs' eCRF at Screening (for Cohort1-3) and on Day 9 (for Cohort 4):

- Height (cm)
- Body Weight (kg)
- Body Mass Index (BMI) (kg/m^2)

The following other baseline data will also be collected:

- Alcohol Breath Test ('Alcohol Breath Test' eCRF)
- Pregnancy Test ('Pregnancy Test' eCRF)
- Serology – hepatitis B surface antigen, hepatitis C antibody titer, and HIV ('Serology' eCRF)
- Urine Drug Screen ('Urine Drug Test' eCRF)

**4.4.5 Medical and surgical History**

Medical history is information about conditions that a subject might have suffered from prior to the administration of study drug, or conditions that were ongoing at the time of the administration of study drug.

Medical and surgical history data will be collected on the 'Medical and Surgical History' eCRF.

**Statistical Analysis Plan**

**Sponsor:** Island Pharmaceuticals Ltd  
**Protocol Number:** ISLA101-P01-CT001

**4.4.5.1 Coding of Medical History Terms**

Medical and surgical history terms (Investigator terms) will be coded to a lowest level term (LLT), preferred term (PT), high level term (HLT), high level group term (HLGT) and a system organ class (SOC) according to the Medical Dictionary for Regulatory Activities (MedDRA) dictionary, Version 26 or later, depending on the latest version available during the study.

**4.4.6 Prior and Concomitant Medications**

Prior and concomitant medications/vaccinations data will be collected throughout the study on the 'Prior and Concomitant Medications' eCRF.

Missing and partial concomitant medications dates will be handled according to the rules specified in Sections 5.1.4 and 5.6.2.

**4.4.6.1 Medication Definitions**

Prior medications are defined as any medication where the use was stopped prior to the first administration of study drug.

Concomitant medications are defined as any medication (other than the study drug) that was used at least once after the first administration of study drug. Medications stopping on the same day as the first study drug administration will be considered as concomitant medications.

**4.4.6.2 Coding of Medication Terms**

Prior and concomitant medication terms will be coded to an anatomical therapeutic chemical (ATC) class term (Level 2) and a preferred medication name based on the active drug substance using the World Health Organization-Drug Dictionary (WHO-DD), Version Global C3, Sep 2023.

**4.4.7 Assignment to Treatment**

Subjects will be randomized to a treatment and the randomization number will be reported on the 'Randomization' eCRF. The randomization information collected on the 'Randomization' eCRF will be listed.

**5. Statistical Methodology****5.1 General Statistical Methods****5.1.1 Software**

All analysis data sets and outputs will be produced by the Biostatistics Department of Resolutum Global using the SAS® Version 9.4 (SAS Institute, Cary, North Carolina, USA) or higher.

The pharmacokinetic concentrations will be processed using standard noncompartmental analytical procedures to derive the required parameters. The software used for the analysis will be Phoenix™ WinNonlin® v8.4.0 or greater (Certara, Princeton NJ, USA).

**5.1.2 Definitions**

The following definitions will be used:

- **Date of the First Study Drug Administration:** The date of the first study drug administration is defined as the earliest date on which study drug was administered as reported on the 'Study Drug Administration' eCRF.
- **Baseline:** The baseline value is defined as the last available valid assessment collected prior to the first study drug administration. Repeat and unscheduled assessments will be included in

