## Statistical Analysis Plan

**Sponsor:** Island Pharmaceuticals Ltd  
**Protocol Number:** ISLA101-P01-CT001

Table 1 Study Procedures and Assessment to Dose Under Fasted (Cohort 1-3) and Fed Condition (Cohort 4)

Study Procedure	Study Period	Cohorts 1-3							Cohort 4							
		Screening	Clinic Check-in	Treatment Period				Follow-up/ET	Clinic Check-in	Treatment Period				Follow-up/ET		
	Study Day	-28 to -2	-1	1	2	3	4	5	8	9 	10	11	12	13	14	17
	Visit Window (days)	N/A		Inpatient					+/-1	+/-3	Inpatient				+/-1	
Informed Consent		X								X						
Inclusion/Exclusion Criteria		X	X							X						
Demographics		X														
Height and weight		X								X						
Medical History		X	X							X						
Vital Signs 		X	X	X	X	X	X	X	X	X	X	X	X	X	X	
12-lead electrocardiogram (ECG) 		X	X	X						X	X					
Full Physical Exam		X	X						X	X					X	
Hep B, Hep C, HIV		X														
Safety laboratory tests (chemistry, hematology, coagulation, urinalysis)		X	X	X	X	X	X	X	X	X	X	X	X	X	X	
Pregnancy test 		X	X						X	X					X	
FSH 		X														
Urine screen for drugs of abuse 		X								X						
Alcohol breath test		X	X							X						
Admission			X							X						

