## Statistical Analysis Plan

**Sponsor:** Island Pharmaceuticals Ltd  
**Protocol Number:** ISLA101-P01-CT001

Study Procedure		Cohorts 1-3						Cohort 4								
	Study Period	Screening	Clinic Check-in	Treatment Period				Follow-up/ET	Clinic Check-in	Treatment Period				Follow-up/ET		
	Study Day	-28 to -2	-1	1	2	3	4	5	8	9 	10	11	12	13	14	17
	Visit Window (days)	N/A	Inpatient				+/-1		+/-3	Inpatient				+/-1		
Study drug administration				X						X 						
High-fat, high-calorie breakfast										X						
PK blood samples 				X	X	X	X	X		X	X	X	X	X		
Adverse events 		X	X	X	X	X	X	X	X	X	X	X	X	X		
Concomitant medication review		X	X	X	X	X	X	X	X	X	X	X	X	X		
Discharge								X						X		

ECG = electrocardiogram; ET = early termination; FSH = follicle-stimulating hormone; Hep = hepatitis; HIV = human immunodeficiency virus; PK = pharmacokinetic(s);

 Vital signs include blood pressure, pulse, respiration and temperature.

 12-lead ECG will be performed in triplicate at screening, and on Day -1 (check-in) to confirm eligibility, and on Day 1 at 5 hours ( $\pm$ 15-minute) post dose. A single ECG will be performed on Day 9 (check-in) and on Day 10 at 5 hours ( $\pm$ 15-minute) post dose.

 A serum pregnancy test will be performed at screening and urine pregnancy test will be performed at check-in and at follow-up for all female subjects.

 For all female subjects to confirm or refute postmenopausal status.

 A nicotine urine or breath test may be utilized for tobacco use testing at site discretion.

 Study drug will be administered approximately 30 minutes after start of a high-fat, high-calorie meal; 100% meal consumption is preferred.

 PK sampling to assess the PK of fenretinide will be performed at the time points as specified in Table 2.

 Monitoring for serious adverse events begins when the informed consent form is signed; and treatment-emergent adverse events begins after the first dose is administered.

 Study day is relative to study drug administration for the subjects in Cohort 3.

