## Statistical Analysis Plan

**Sponsor:** Island Pharmaceuticals Ltd  
**Protocol Number:** ISLA101-P01-CT001

the derivation of the baseline values. Results including, but not limited to, 'Not done', 'Not applicable', 'Unknown' will not be included in the baseline derivations.

Baseline calculation for the ECG parameters will be based on the mean value of the triplicate ECG reading at baseline visit for Cohort 1-3.

- **Change from Baseline:** The change from baseline value is defined as the difference between the result collected/derived at a post-baseline visit and the baseline value (for that specific period for changes from the baseline values).

The change from baseline value at each post-baseline visit will be calculated for all continuous parameters using the following formula:

$$\text{Change from Baseline Value} = \text{Result at Post-Baseline Visit} - \text{Baseline Value}$$

The change from baseline value will only be calculated if the specific post-baseline result and the baseline value for the parameter are both available and will be treated as missing otherwise. In the data listings, the change values will be set to '-' (not applicable) for pre-baseline assessments.

- **Study Day:** The study day of an event is defined as the relative day of the event starting with the date of the first study drug administration (reference date) as Day 1 (there will be no Day 0).

The study day of events occurring before the study drug administration will be calculated as:

$$\text{Study Day} = (\text{Date of Event} - \text{Date of Study Drug Administration})$$

For events occurring on or after Day 1, study day will be calculated as:

$$\text{Study Day} = (\text{Date of Event} - \text{Date of Study Drug Administration}) + 1$$

Study days will only be calculated for events with complete dates and will be undefined otherwise.

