**Table 7 Study Visits**

Actual Visit	Summary Table Treatment Label	By-subject Listing Treatment Label
Screening		Screening
Day -1 – Clinic Check-In	Baseline	Day -1
Day 9 -Clinic Check-In		Day 9
Day 1	Day 1	Day 1
Day 10		Day 10
Day 2	Day 2	Day 2
Day 11		Day 11
Day 3	Day 3	Day 3
Day 12		Day 12
Day 4	Day 4	Day 4
Day 13		Day 13
Day 5 - Discharge	Day 5	Day 5
Day 14 - Discharge		Day 14
Day 8 – Follow Up/ET	Follow-up	Day 8 – Follow UP
Day 17 – Follow Up/ET		Day 17 – Follow Up
Unscheduled		Unscheduled
		Early Termination*

\*If early termination occurred, the visit labels “Day 8 – Follow Up” and “Day 17 – Follow Up” will be marked as “Early Termination”.

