### 6.8.3 Laboratory Parameters

The laboratory parameters described in Section 4.1.3 will be summarized and listed.

The summary tables of hematology, coagulation and biochemistry results will present summary statistics for each laboratory parameter within the specific test panel by treatment group. For each parameter, summaries will be presented for the baseline and each scheduled post-baseline visit. In addition, summaries will be presented for the change from baseline values at each scheduled post-baseline visit. Refer to Section 4.1.3 for the handling of character results.

The summary of hematology, coagulation, and biochemistry shift tables will present summaries for the shifts in the result classifications ('Normal', 'Low', 'High') from the baseline to each of the scheduled post-baseline visit for each parameter with a defined reference range, within the specific test panel.

The listings of hematology, coagulation and biochemistry data will include all laboratory data (collected at scheduled and unscheduled visits) in the clinical database. The listings will present all the information (fields) that is available in the laboratory dataset. In addition, the observation that was used as the baseline records (values) for each parameter will be flagged, the change from baseline value and the derived result classification (based on the normal ranges where applicable) at each post-baseline visit will be presented.

The summary of urinalysis table will present the number and percentage of subjects for each of the result classifications (Normal, Abnormal NCS and Abnormal CS) for the baseline, each scheduled post-baseline per parameter.

The listing of urinalysis (including microscopy) data will include all laboratory data (collected at scheduled and unscheduled visits) in the clinical database. The listings will present all the information (fields) that is available in the laboratory dataset. In addition, the observation that was used as the baseline record (value) for each parameter will be flagged.

The FSH parameters will be listed as part of the pregnancy listing.

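### SAP 5.1.2 and nine of ten Fasted/Fed safety shells place baseline before the fasted dose, in conflict with the period baseline used elsewhere in the same SAP

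*SAP*

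**What the plan says.** SAP 5.1.2 gives two rules that cannot both hold for a subject dosed twice.

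- Baseline: "The baseline value is defined as the last available valid assessment collected prior to the first study drug administration". The date of first administration is "defined as the earliest date on which study drug was administered". Dosing is on Day 1 (fasted) and Day 10 (fed), so for a recalled subject that date is Day 1.
- Change from Baseline: the post-baseline result is compared with "the baseline value (for that specific period for changes from the baseline values", which is a period baseline.

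For ECG, 5.1.2 bases baseline on the "mean value of the triplicate ECG reading at baseline visit for Cohort 1-3" and gives no rule for Cohort 4. SAP Table 1, footnote 2, provides only one tracing there: "A single ECG will be performed on Day 9 (check-in) and on Day 10 at 5 hours".

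For laboratory shifts, SAP 6.8.3 tabulates movement "from the baseline to each of the scheduled post-baseline visit for each parameter with a defined reference range", with no mention of period.

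SAP 5.1.5 says that Tables 5 to 7 supply the labels for the outputs. In Table 7 the row "Day 9 -Clinic Check-In" follows Day -1 and appears to share its Baseline label, just as Day 10 follows Day 1. In the text available for this review the Day 9 label cell is blank, so the shared label is an inference. SAP section 7 does not address the conflict.

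**The concern.** The Fasted/Fed safety tables exist to set the same subjects' two periods side by side. If the fed block uses a baseline from before the fasted dose, its Baseline row is a copy of the fasted one. Anything left over from the fasted period, or any drift between the periods, is then presented as change during the fed period. Programmers work from definitions and footnotes, and here most of these state the first-dose rule. Without a correction, the fed baseline would be settled at programming, possibly differently from table to table.

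**Working it through.** No figure in the plan has to be reproduced. The check compares the footnotes and works through what the literal rule does.

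**Footnote count.** Ten Fasted/Fed safety shells define a baseline.

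- First-dose wording, results with change from baseline: 14.3.4.1.1.2 (hematology), 14.3.4.2.1.2 (biochemistry), 14.3.4.3.1.2 (coagulation), 14.3.5.2 (vital signs) = 4.
- First-dose wording, shifts: 14.3.4.1.2.2, 14.3.4.2.2.2, 14.3.4.3.2.2 = 3.
- First-dose wording, by-visit categories: 14.3.4.4.1.2 (urinalysis), 14.3.6.2.2 (ECG overall assessment) = 2.
- Period wording: 14.3.6.1.2 (ECG results) = 1.

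4 + 3 + 2 = 9 of 10 use the first-dose wording. The two ECG shells therefore define different baselines for the same Day 9 and Day 10 recordings.

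**Listings.** Seven by-subject listings carry the first-dose footnote: 16.2.8.1 to 16.2.8.4, 16.2.9.1, 16.2.9.2.1 and 16.2.9.2.2. Listing 16.2.9.2.1 could thus show fed ECG changes that disagree with Table 14.3.6.1.2.

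**Timing.** There is no Day 0, so Day -1 to Day 1 is 1 day and Day 1 to Day 10 is 9 days. A Day -1 baseline lies 1 + 9 = 10 days before the fed dose. With the +/-3 day window on Day 9, and assuming dosing the day after check-in, the range is 7 to 13 days. A pre-dose Day 1 value would lie 9 days before (6 to 12). The Day 9 value lies 1 day before.

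**Effect on changes.** For a fed-period result Y, with Day -1 and Day 9 as the two candidate baselines, the literal change is Y - B(Day -1) and the period change is Y - B(Day 9). They differ by B(Day 9) - B(Day -1), the same amount at every fed visit. The documents give no figure for this difference; if it is zero, the readings agree.

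**Effect on shifts.** Take an illustrative subject (assumed values) with ALT 0.9 x ULN at Day -1 and 1.3 x ULN at Day 9 and Day 11. The literal rule gives Normal to High; the period rule gives High to High. With all subjects returning and assessed, the Normal-to-High cell gains 1/6 = 16.7% on active or 1/2 = 50% on placebo, and the High-to-High cell loses the same amount. If only 5 or 4 active subjects return, the figure is 1/5 = 20.0% or 1/4 = 25.0%; the protocol synopsis provides a separate consent form for Cohort 4. The post-baseline High total is the same under both rules.

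**Could such a subject be dosed?** Yes. Eligibility is rechecked at Day 9 (SAP 4.4.2), but protocol inclusion criterion 9 (section 4.2) accepts out-of-range values judged not clinically significant, and exclusion criterion 6 (section 4.3) concerns only liver tests above 1.5 x ULN. SAP 4.1.3 classifies Low and High by the normal range alone.

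**The case against.** The best reply is that the intent is plain and the slip editorial. Table 7 appears to make Day 9 the fed Baseline visit, and 5.1.5 ties the outputs to that table. SAP 6.8.4 speaks of baselines in the plural. SAP 4.4.4 collects baseline height, weight and BMI on Day 9 for Cohort 4. Limiting the triplicate rule to Cohorts 1-3 fits a separate single-tracing baseline in Cohort 4. Safety analysis is descriptive, the primary objective concerns fasted dosing, and raw values are all listed. The fasted block of the shift tables runs to follow-up, so an abnormality persisting at Day 8 would be visible beside the fed block.

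Much of this stands. A period baseline was probably intended, and the consequence is modest. But Table 7 assigns visit labels; it does not say which record is the baseline. The explicit definition and nine footnotes say the opposite. The period wording under Change from Baseline concerns continuous parameters, so it does not settle the shift tables. The listings show raw values, but their baseline footnotes carry the same first-dose rule.

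A further objection concerns the remedy: a value taken before dosing on Day 10 could serve as baseline and also appear in the row labelled Day 1. Protocol 8.2.1 has temperature taken before dosing on dosing days, so this is a fair point for the edit to cover.

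**Conclusion.** The conflict is real and should be corrected, though it is not critical. As written, the definition and nine of ten shells give fed-period summaries a pre-fasted baseline, against the SAP's own period rule. In the shift tables the size is one subject in the wrong baseline column: 1 of 6 active or 1 of 2 placebo, assuming all return. In the change tables it is the Day 9 minus pre-fasted difference, which is unknown. In the urinalysis and ECG overall shells only the fed Baseline row is affected.

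Three stronger readings are tempting and not supported. A reader might infer that the count of abnormal fed values is inflated; it is not, because post-baseline totals are the same under either rule. A reader might infer that the food-effect conclusion is at risk; the PK analysis does not use this baseline, and the fasted Cohort 1-3 tables are unaffected because each subject there has one dose. A reader might infer a deliberate choice of a first-dose baseline; the surrounding text points the other way.

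**What to change.** In SAP 5.1.2, define baseline for each period as the last valid assessment before that period's dose, consistent with Table 7, and name the single Day 9 ECG as the Cohort 4 ECG baseline. State that a dosing-day value used as baseline is not also tabulated as post-baseline. Align footnote [1] in the nine Fasted/Fed shells and the seven by-subject listings with Table 14.3.6.1.2. In the same edit, relabel the second active block as Fed in Tables 14.3.4.1.1.2, 14.3.4.2.1.2 and 14.3.4.3.1.2, where both active blocks now read Fasted.

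The cost is SAP and shell wording only: Day 9 laboratory tests, vital signs and ECG are already scheduled. The one loss is that the fed tables will no longer show cumulative change from the drug-free state. That change can still be derived from the listed values.
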